### 5.8.3. 6-Minute Walk Test

The distance walked at each visit and the change from baseline at each post baseline visit, as obtained from the 6-minute walk test (6MWT), will be summarized descriptively for ambulatory subjects with non-missing baseline 6MWT assessments. The distance walked at each will also be summarized for each actual age.

### 5.8.4. Timed Function Tests

Timed function test data (ie, time to stand from supine, time to run/walk 10 meters, time to climb 4 stairs, and time to descend 4 stairs) and change from baseline to each post baseline visit will be summarized descriptively by visit for ambulatory subjects with non-missing baseline timed function tests assessments. Similarly the time to stand from supine, time to run/walk 10 meters, time to climb 4 stairs, and time to descend 4 stairs will also be summarized for each actual age.

Timed function test (TFT) data imputation rules as the following will be used in the summary.

- If time to run/walk 10 meters > 30 sec, then set to 30 sec.
- If time to stand from supine > 30 sec, then set to 30 sec.

The Kaplan-Meier method will be applied to the analysis of age at loss of ambulation. The median age at loss of ambulation will be reported by treatment group in studies 020/020e (ataluren/ataluren, placebo/ ataluren, and overall), corticosteroid use duration (<12 months,  $\geq$ 12 months), and corticosteroid type (deflazacort vs prednisone/prednisolone) at baseline. The Kaplan-Meier curves will also be displayed. The age at loss of ambulation is defined as age of the disease progression reported as the adverse event. The subjects who are ambulatory at the end of study or discontinuation will be censored on the last valid visit date. Age on that date will be used in the analysis.

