10.5.2. Timed Function Tests (TFTs)

The results of the timed function tests (the time taken to stand from a supine position, time taken to run/walk 10 meters, and time taken to climb/descend 4 standard-sized stairs) in those patients who have the ability, as well as the changes from baseline will be described by patient and visit and summarized by visit and overall. The within patient changes from baseline will be tested for each applicable visit using the paired t-test. Patients who cannot perform a test within 30 seconds will be assigned 30 seconds as their result.

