## **7. ANALYSIS CHANGES FROM PROTOCOL**

The supportive analyses on 6-minute walk test have been removed because they are not of the scientific interest any more after the early termination of the study. All paired t-tests have been removed.

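### SAP 5.8.4 narrows the protocol's 30-second rule to two of the four timed function tests and does not say what value a boy gets when he can no longer do a test

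*SAP*

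**What the plan says.** Protocol 10.5.2 names standing from supine, the 10-metre run/walk, and climbing and descending four stairs. It ends with one rule for all of them: "Patients who cannot perform a test within 30 seconds will be assigned 30 seconds as their result". The same section introduces the results as those "in those patients who have the ability, as well as the changes from baseline will be described by patient and visit".

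SAP 5.8.4 summarises the same four tests: "time to stand from supine, time to run/walk 10 meters, time to climb 4 stairs, and time to descend 4 stairs". The tables are "summarized descriptively by visit for ambulatory subjects with non-missing baseline timed function tests assessments", and there are further summaries by age. The SAP then states: "Timed function test (TFT) data imputation rules as the following will be used in the summary". Two rules follow and no others:

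- The first covers the run/walk: "If time to run/walk 10 meters > 30 sec, then set to 30 sec"
- The second covers rising from the floor: "If time to stand from supine > 30 sec, then set to 30 sec"

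SAP 5.1 fixes ambulatory status at baseline unless otherwise specified. SAP 1 gives the SAP precedence over the protocol where the two conflict. SAP 7 lists two changes from the protocol. One is "The supportive analyses on 6-minute walk test have been removed"; the other is the removal of all paired t-tests. The timed-test rule is not mentioned.

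**The concern.** On a timed test, losing the ability to do the task is the worst outcome, and in this disease it is expected to become more common over up to 144 weeks of treatment. A boy who was ambulatory at baseline with a valid baseline time stays in the analysis set when he loses the ability. Without an assigned value, however, he adds nothing to the visit mean or the mean change. The missingness is then related to the outcome and likely to grow over time, so later means would tend to describe the boys still able to do the test.

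The SAP avoids this for the North Star Ambulatory Assessment. SAP 5.8.5 scores zero for an activity that disease progression or loss of ambulation prevents. The timed tests have no equivalent. Stair climbing has neither a cap nor an inability rule, although Protocol 14.2 reports it as the timed test with the largest effect in Study 007.

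**Working it through.** The plan states no figure that depends on this rule, so there is nothing to reproduce. The check is a comparison of the two texts, followed by an illustration of size.

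**Rule by rule**

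| Test | Protocol 10.5.2 | SAP 5.8.4: time above 30 s | SAP 5.8.4: unable, no time |
|---|---|---|---|
| 10-metre run/walk | 30 s | 30 s | not stated |
| Stand from supine | 30 s | 30 s | not stated |
| Climb 4 stairs | 30 s | no rule, enters uncapped | not stated |
| Descend 4 stairs | 30 s | no rule, enters uncapped | not stated |

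The protocol's rule covers 4 of 4 tests and the SAP's covers 2 of 4. An explicit rule for inability without a time appears for 0 of 4 tests in the SAP.

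**Visit mean**

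Let f be the share of boys unable at a visit with no recorded time, and m the mean time of those still able. The documents give neither, so both are assumptions.

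- SAP as written: mean = m
- Protocol rule: mean = (1 − f) × m + 30 × f
- Gap = f × (30 − m)

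For m = 6 to 12 s:

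- f = 5%: 0.05 × 24 = 1.2 s down to 0.05 × 18 = 0.9 s
- f = 10%: 0.10 × 24 = 2.4 s down to 0.10 × 18 = 1.8 s
- f = 20%: 0.20 × 24 = 4.8 s down to 0.20 × 18 = 3.6 s

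**Mean change from baseline**

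Let b be the baseline time of the boys who become unable and c the mean change in the able boys, both assumed.

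- SAP as written: mean change = c
- Protocol rule: mean change = (1 − f) × c + f × (30 − b)
- Gap = f × (30 − b − c)

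With b = 12 s and c = 2 s the gap is 16 × f:

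| f | SAP | Protocol rule | Gap |
|---|---|---|---|
| 5% | 2.0 s | 2.8 s | 0.8 s |
| 10% | 2.0 s | 3.6 s | 1.6 s |
| 20% | 2.0 s | 5.2 s | 3.2 s |

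**Yardstick**

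Protocol 14.2 cites about 1.5 s as a clinically meaningful difference on these tests. That figure concerns ataluren against placebo in Study 007, so here it only gives a sense of scale.

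- Visit mean: the gap reaches 1.5 s at f = 1.5/24 = 6.25% (m = 6 s) to 1.5/18 = 8.3% (m = 12 s).
- Mean change: it reaches 1.5 s at f = 1.5/21 = 7.1% (b = 8 s, c = 1 s) to 1.5/7 = 21.4% (b = 20 s, c = 3 s).

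**Opposite effect on the stair tests**

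If nobody is unable but a share g of boys has recorded stair times above 30 s, averaging t, the SAP mean exceeds the protocol-rule mean by g × (t − 30). A missing cap therefore pushes the stair means up, while dropped boys pull them down. The documents give no data to say which effect is larger.

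**The case against.** The strongest reply is that a reader might infer from SAP 5.8.4 that unable boys are removed from all four tests and that decline is certainly understated. The documents do not support that.

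- **Silence.** The SAP never says these boys are excluded. It overrides the protocol only in a conflict, so the protocol's 30-second sentence could be read as filling the gap. This stands as an ambiguity. Against it, the SAP gives a specific, shorter list of rules for the summary, and a programmer would most naturally implement that list.
- **Coding.** No section says how inability is recorded, and the detailed test instructions are in a Study Manual that is not part of these documents. If inability is entered as a time above 30 s, the two SAP rules work as the protocol intends for 10 metres and supine. This stands. It does not help the stair tests, which have no cap.
- **The protocol's own wording.** Protocol 10.5.2 confines the results to patients with the ability, then assigns 30 s to those who cannot perform in time. A summary of able boys is one possible reading. However, Protocol 10.5.1 defines nonambulatory as being unable to complete the 10-metre test in 30 s or less, which suggests that such wording includes inability. On either reading the stair tests lose the 30-second rule.
- **Other evidence of loss.** SAP 5.8.4 has a Kaplan-Meier analysis of age at loss of ambulation, the NSAA scores inability as zero, and each table shows n and the median. A falling denominator would therefore be visible. This reduces the harm but does not correct the means.
- **Limited use.** The primary endpoint is safety. SAP 8.1 leaves the stair tests out of the natural-history endpoints. The comparisons specified in SAP 8.3 are FVC and age at loss of ambulation, and the latter already counts a 10-metre time above 30 s as an event. This stands.

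**Conclusion.** The SAP narrows the protocol's rule without declaring it. For stair climb and descend the 30-second value is gone: long recorded times enter uncapped and inability has no value. For 10 metres and supine, boys who cannot do the test drop out only if inability is not coded as a time above 30 s, and the documents leave that open.

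Where boys do drop out, the set fixed at baseline means later visit means and changes tend to understate decline. Under the assumed inputs, the visit mean is 1.8 to 2.4 s too low at 10% unable, and the mean change is 0.8 to 3.2 s too low at 5% to 20% unable. These sizes are illustrations, because the documents give neither the share unable nor the mean times.

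A reader might go further and infer that a formal efficacy result is compromised. It is not: these are descriptive secondary summaries in a single-arm extension with the paired t-tests removed, so no test or error rate is affected. The point deserves correction because these are named secondary endpoints and the remedy is small.

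**What to change.** In SAP 5.8.4, replace the two rules with one for all four tests: assign 30 s when the time exceeds 30 s, or when the test cannot be performed because of disease progression or loss of ambulation. The inability condition is taken from the SAP's NSAA rule and is more explicit than the protocol's sentence. State how inability is identified in the data.

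Leave tests missing for other reasons as missing. Report the number of boys assigned 30 s at each visit for each test. List any remaining departure from Protocol 10.5.2 in SAP 7.

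The cost is a short wording change, one derivation and one extra row per table. Reported decline may be larger. The 30-second value also creates a ceiling, so the median should be shown alongside the mean.

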### 8.3. Analyses Based on Matched Populations of CINRG and Study 020e

Demographics and baseline characteristics (age, race, ambulation status, corticosteroid use (yes or no), duration of corticosteroid use, corticosteroid type, baseline 6MWD, baseline time to run/walk 10 meters, baseline time to stand from supine, baseline %-predicted FEV1, %-predicted FVC, PEF, NSAA total score) will be summarized descriptively for CINRG and Study 020e

based on each matched population. The summary will be displayed by corticosteroid use (yes vs no) and cumulative steroid use ( $\geq 12$  months vs  $< 12$  months) for baseline ambulatory and non-ambulatory subjects separately. The baseline is defined as the first visit in CINRG data. The comparison to the natural history data (ie, CINRG data) based on matched subjects will be performed in FVC using piece-wise regression models and age to loss of ambulation using Kaplan-Meier method.

Piece-wise regression models will be applied to log FVC in CINRG and study 020e data, separately, using different ages as the changepoint. The most possible changepoint in terms of age will be chosen at the best model fit (ie, AICC value is the maximal). Scatter plots of log FVC and the most fitted piece-wise regression line will be generated for CINRG and study 020e, separately. Comparison between the observed and predicted FVC in study 020e will be performed using repeated measures analysis of variance to account for within-subject correlation, where the predicted values are based on the regression equation estimated by the best fit regression model based on CINRG data.

In study 020e, the loss of ambulation is defined as the disease progression reported as the adverse event or the time to run/walk 10 meters  $> 30$  seconds, whichever occurs earlier. The event age is the one on the AE start date. The subjects who are ambulatory at the end of study will be censored on the last valid timed function tests assessment date. Age on that date will be used in the analysis. In the CINRG data, the age at the earliest report of the non-ambulation or the time to run/walk 10 meters  $> 30$  seconds, whichever earlier, will be picked as the event age. If subjects in CINRG data do not report non-ambulation, the age at the last report of ambulation will be chosen as the censor age. A sensitivity analysis will be performing based on the loss of ambulation defined only by disease progression AE.

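### SAP 5.8.4 takes age at loss of ambulation from a disease-progression AE alone, which SAP 8.3 ranks as the sensitivity version, and neither age-scale Kaplan-Meier analysis states delayed entry

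*SAP*

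**What the plan says.** SAP 5.8.4 applies Kaplan-Meier to age at loss of ambulation. The event is given in one sentence: "The age at loss of ambulation is defined as age of the disease progression reported as the adverse event". The median "will be reported by treatment group in studies 020/020e" and by corticosteroid duration and type. Boys still walking "will be censored on the last valid visit date". No timed-test criterion, entry age or ambulatory restriction is stated.

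SAP 8.3 plans the same outcome for the comparison with the CINRG natural history data. There, "the loss of ambulation is defined as the disease progression reported as the adverse event or the time to run/walk 10 meters" above 30 seconds, whichever is earlier. It adds: "A sensitivity analysis will be performing based on the loss of ambulation defined only by disease progression AE". Boys still walking "will be censored on the last valid timed function tests assessment date". SAP 8.2 limits this analysis to boys aged 7-14 and ambulatory at entry. Section 8.3 also names Kaplan-Meier on age without mentioning delayed entry.

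SAP 1 keeps the Section 8 analysis out of the clinical study report. SAP 5.1 to 5.3 expect both ambulatory and nonambulatory boys at entry. SAP 5.2 records that the sponsor has decided to discontinue the study.

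**The concern.** There are two separate problems.

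The first is the event. The report would carry only the AE-only median, although the same SAP treats that version as secondary wherever it has both. A boy who takes more than 30 seconds over 10 m, but has no progression AE, is not an event in 5.8.4. In the other direction, the AE is not limited in words to loss of walking. Protocol 8.1.2 has expected progression of the dystrophinopathy reported as an AE without naming a function, so an AE for some other decline could be counted.

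The second is the time scale. A boy who enters at 12 still walking could not have been recorded as losing ambulation at 9. If he is counted in the risk set at 9, the estimated risk at that age is diluted and the median moves later. An absolute median age at loss of ambulation invites comparison with natural history, so a shift of about a year would matter to its reading.

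**Working it through.** **Event definitions side by side**

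| | SAP 5.8.4 (in the report) | SAP 8.3 (outside the report) |
|---|---|---|
| Event | Progression AE only | Earlier of progression AE or 10 m run/walk >30 s |
| AE-only version | The only analysis | Sensitivity analysis |
| Censoring | Last valid visit | Last valid timed function test |
| Population | No restriction stated | Aged 7-14 and ambulatory at entry (8.2) |
| Delayed entry | Not stated | Not stated |

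**Why ordinary Kaplan-Meier is late.** At each event age t the survival estimate is multiplied by 1 − d/n. With delayed entry, n counts boys with entry age < t ≤ exit age. Without it, n also counts every boy who enters after t. The numerator d is unchanged, so each step is too small and the curve reaches 0.5 too late.

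**Size.** The documents give no expected median, event count or entry-age distribution, so there is no planned figure to reproduce. The inputs are therefore:
- From the documents: entry age 7-14 and ambulatory at entry (SAP 8.2), and follow-up of 144 weeks, that is 144 × 7 / 365.25 = 2.76 years (Protocol 6.2.1).
- Assumed: n = 200 (Protocol 10.1 gives an upper bound of about 220), uniform entry among boys still walking, and normal age at loss with mean 12, 13 or 14 and SD 2, 2.5 or 3 years. Protocol 2.1 puts wheelchair dependence for most boys at 10-14.

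Median over 300 simulated data sets at 2.76 years, ordinary / delayed entry:

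| True median | SD 2 | SD 2.5 | SD 3 |
|---|---|---|---|
| 12 | 12.89 / 12.02 | 13.23 / 12.09 | 13.55 / 12.17 |
| 13 | 13.68 / 13.00 | 13.92 / 13.01 | 14.16 / 13.11 |
| 14 | 14.42 / 13.99 | 14.60 / 14.02 | 14.77 / 14.07 |

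The smallest error is 14.42 − 14 = 0.42 years and the largest 13.55 − 12 = 1.55 years. On the same grid at 2 years of follow-up, the range is 14.52 − 14 = 0.52 to 13.79 − 12 = 1.79 years.

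Effect of follow-up, with true median 13 and SD 2.5:

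| Follow-up (years) | Ordinary | Delayed entry | Ordinary median not reached |
|---|---|---|---|
| 2.76 | 13.90 | 12.99 | 0% |
| 2 | 14.07 | 13.00 | 0% |
| 1.5 | 14.21 | 13.01 | 3% |
| 1 | 14.28 | 13.00 | 26% |

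**Event capture (assumed rates, same base case, no delayed entry, 2.76 years).** If 5, 10, 20 or 30% of losses have no progression AE, the median is 14.02, 14.18, 14.48 or 14.88. If progression AEs for other declines occur at 2, 5 or 10 per 100 boy-years and are counted, it is 13.78, 13.54 or 13.21. Against 13.90, the two faults pull in opposite directions.

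**Boys nonambulatory at entry.** If 10% of boys had already lost ambulation (assumed to have happened in the preceding 48 weeks), the ordinary median is 14.36 when they are censored at last visit, 13.56 when counted as events at entry age, and 13.93 when excluded. All three stay above 13.0, but they span 0.8 years on a choice that 5.8.4 does not make.

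**CINRG comparison.** With the same loss distribution and entry ages 7-14, a control cohort followed for 5 or 8 years has ordinary medians of 13.74 and 13.70. The spurious difference is about 0.2 years with 2.76 years of 020e follow-up (13.90 − 13.70 = 0.20) and up to 0.4 years with 2 years (14.07 − 13.70 = 0.37). With delayed entry all these medians are 13.0-13.1.

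**The case against.** The strongest reply is that 5.8.4 is silent on delayed entry rather than opposed to it, that the shift was computed under the 8.2 restriction, which 5.8.4 does not state, and that the output is descriptive, in a study whose primary objective is safety. Age at loss of ambulation is not a listed endpoint in the protocol or the SAP. A composite event in 8.3 may also be deliberate, because it parallels the rule used for CINRG. All of this limits the weight of the point. It does not explain why the report should carry only the version that 8.3 ranks second, or tell a programmer which boys are at risk from what age.

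Several stronger readings are tempting, and the documents do not support them:
- A reader might infer that the rule "If time to run/walk 10 meters > 30 sec, then set to 30 sec" makes the 8.3 criterion impossible to meet. SAP 5.8.4 limits that rule to its own summary, and 8.3 needs recorded times.
- A reader might infer from "The event age is the one on the AE start date" that 8.3 dates a failed test at a later AE. The wording that the earlier event counts settles this, although the test date should be written out.
- A reader might infer that follow-up starts in Study 020 while events come only from 020e. No passage proposes this. SAP 1 and 4 tie the data and population to the extension, and 020/020e names treatment sequences.
- A reader might make much of the two censoring dates. Timed tests are scheduled at every treatment visit, so for boys still being tested the dates differ by about the six-week post-treatment visit.
- A reader might infer that the boy with a failed test and no AE falls outside every rule. On 5.8.4's own terms he is censored as walking. The fault is that his loss is missed.

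**Conclusion.** The point holds and should be fixed. The mismatch between 5.8.4 and 8.3 is plain in the text. For boys ambulatory at entry, an age-scale Kaplan-Meier without delayed entry gives a median that is too late, by about 0.4 to 1.6 years at 144 weeks under the assumed inputs, and by more as follow-up shortens. The size rests on those assumptions and on the program following the text without an entry age.

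Three limits apply. The direction of error in 5.8.4 as written is not fixed, because neither the relevant AEs nor the handling of boys already nonambulatory is settled. Most of the entry effect cancels in the CINRG comparison if entry ages and follow-up are alike. A reader might also infer a bias between ataluren/ataluren and placebo/ataluren, but none is shown.

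**What to change.** In 5.8.4, adopt the 8.3 event: the earlier of an AE that specifies loss of ambulation, or a recorded 10 m run/walk above 30 seconds taken before any 30-second cap, dated at whichever comes first. Tighten the AE wording in 8.3 in the same way. Make AE-only the sensitivity analysis in both sections, and use one censoring date.

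In both sections, restrict to boys ambulatory at the start of observation and use delayed entry at that age. The start is first dose in 020e if only 020e data are used, and first visit for CINRG. Show numbers at risk by age.

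The cost is SAP wording and reprogramming on data already collected. The median is likely to be less favourable. It is also somewhat more variable: the SD across simulated data sets at 2.76 years was about 0.3-0.5 years, against 0.25 without delayed entry. The curve is unstable at young ages, where few boys are at risk.

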### **5.8.5. North Star Ambulatory Assessment**

The NSAA consists of 17 activities, each scored as 0, 1, or 2. The sum of these 17 scores will be used to form a total score. If fewer than 13 of the 17 activities are performed, the total score will be considered missing. If from 13 to 16 activities are performed, the total score will be calculated by multiplying the sum of the scores in the x activities that were performed by 17/x. If an activity cannot be performed due to disease progression/loss of ambulation, a score of zero will be assigned. The linear score is a transformation of the NSAA score to a scale of 0 to 100 [Mayhew 2013].

Total scores and linear scores from the North Star Ambulatory Assessment will be summarized by visit and change from baseline to each post baseline visit will be summarized descriptively for ambulatory subjects with non-missing baseline NSAA assessments. Similarly the total and linear scores will also be summarized for each actual age.

The number and proportion of loss of function of each North Star Ambulatory Assessment item at week 48 will be tabulated. The function loss defined as a shift from non-zero at baseline to zero at week 48. The missing data will be handled by last observation carried forward (LOCF).

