7.2.4. End of Treatment

The patient will return to the clinical research facility at Week 144 (Visit 13) for the End-of-Treatment visit. If the patient discontinues prematurely (ie, before Week 144), and the procedures that would normally be performed at Week 144 should be performed as a Premature-Discontinuation Visit before the patient leaves the study. If the patient terminates the study early because ataluren is commercially available in that country then the patient does not need to come in for the 6-week Post-Treatment Follow-up Visit.

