13.4.3. North Star Ambulatory Assessment

The NSAA is a functional scale specifically designed for ambulant DMD boys. The scale has been developed and piloted in the United Kingdom by the North Star Clinical Network for Paediatric Neuromuscular Disease Management with good intra and interobserver reliability and has recently been used in a large multicenter study [Mazzone 2011].

The scale includes items assessing abilities that are necessary to remain functionally ambulant, ie, ability to rise from the floor, ability to get from lying to sitting and sitting to standing, and that are known to progressively deteriorate in untreated DMD patients. The scale also includes items assessing head raise and standing on heels that can be partly present in the early stages of the disease and a number of activities such as hopping, jumping, and running [Mazzone 2010].

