## 5.2. Subject Disposition

A summary of subjects who discontinued ataluren treatment prematurely or were removed from the study prematurely will be reported for overall subjects and a subgroup of ambulatory/non-ambulatory subjects at study entry. Reasons for treatment early discontinuations will be described.

Since the sponsor has decided to discontinue the Study 020e, subjects who discontinue the study due to this reason or complete the study per protocol will be considered as censored in the time to discontinuation analysis. The time to discontinuation (in weeks) is calculated as  $(\text{discontinuation date} - \text{first dose date} + 1)/7$  for subjects who discontinue from the study due to reasons other than sponsor's decision of termination the study or transitioning to commercial drug. For subjects who discontinue due to these reasons or complete the study, the censor time is  $(\text{discontinuation date} - \text{first dose date} + 1)/7$  and  $(\text{study completion date} - \text{first dose date} + 1)/7$ , respectively. Time to discontinuation will be assessed using Kaplan-Meier methods and the Kaplan-Meier curve will be displayed.

The protocol deviations will be summarized by type. A listing of protocol deviations will be provided.

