## 6. DATA HANDLING

### 6.1. Analysis Visits based on Visit Windows

Since some subjects had early terminations or unscheduled visits in during, the derived analysis visits will be generated by visit window defined as follows. For the 6 weeks post-treatment visit, assign AVISITN=14 and AVISIT=6-Weeks Post-Treatment.

Let Study day=assessment date –first dose date +1.

Study Day	AVISITN	AVISIT
Study Event='SCR' or < study day $\leq$ 1	1	Baseline
1 < study day $\leq$ 126	2	Week 12
126 < study day $\leq$ 210	3	Week 24
210 < study day $\leq$ 294	4	Week 36
294 < study day $\leq$ 378	5	Week 48
378 < study day $\leq$ 462	6	Week 60
462 < study day $\leq$ 546	7	Week 72
546 < study day $\leq$ 630	8	Week 84
630 < study day $\leq$ 714	9	Week 96
714 < study day $\leq$ 798	10	Week 108
798 < study day $\leq$ 882	11	Week 120
882 < study day $\leq$ 966	12	Week 132
966 < study day	13	Week 144

If there are more than 1 valid assessment within one visit window, the last one will be chosen as the analysis value.

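### For Week 48 NSAA item loss, LOCF freezes the last score when data are missing for reasons other than recorded inability; this generally understates loss, and no other analysis is shown beside it

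*SAP*

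**What the plan says.** The analysis is in SAP section 5.8.5: "The number and proportion of loss of function of each North Star Ambulatory Assessment item at week 48 will be tabulated". Loss is defined as follows: "The function loss defined as a shift from non-zero at baseline to zero at week 48". The missing-data rule is one sentence: "The missing data will be handled by last observation carried forward (LOCF".

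Earlier in the same section there is a scoring rule that works in the other direction: "If an activity cannot be performed due to disease progression/loss of ambulation, a score of zero will be assigned".

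Three other places bear on how often LOCF is used:

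- SAP section 6.1 opens the Week 48 window at "294 < study day" and closes it at day 378. The last valid value in the window is used.
- Protocol section 7.2.4 says that for a boy who stops early "the procedures that would normally be performed at Week 144 should be performed as a Premature-Discontinuation Visit before the patient leaves the study". Protocol section 7.17 includes the NSAA at that visit.
- SAP section 5.2 records a cause of missing data unrelated to decline: "Since the sponsor has decided to discontinue the Study 020e". It also mentions transfer to commercial drug.

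The SAP does not say whether a baseline score may be carried forward when there is no post-baseline NSAA. It does not say how the zero rule applies to a boy who has already left. It plans no observed-case or other sensitivity analysis for this table. Protocol section 10.5.3 plans neither the item-loss table nor LOCF, and SAP section 7 does not list them as changes.

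**The concern.** Protocol section 13.4.3 describes the abilities the NSAA measures as ones "that are known to progressively deteriorate in untreated DMD patients". Carrying a non-zero score forward assumes the opposite for the unobserved interval: that nothing further is lost before Week 48. A boy last seen at Week 12 with an item intact is entered at Week 48 as having kept it.

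The SAP also does not ask for the number of imputed values. SAP section 5.1 promises N, n and percentages for categorical tables, but under LOCF a carried-forward boy sits in N beside a boy who was examined. A reader cannot tell observed retention from assumed retention. At stake is the accuracy of 17 descriptive item-loss proportions, not a hypothesis test.

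**Working it through.** The plan states no item-loss rate, missing-data rate or expected result for this table, so there is no figure to reproduce. What follows is an illustration on assumed inputs.

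**Inputs (all assumed)**

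- p: true proportion losing an item by Week 48 (20% unless stated).
- m: share with no NSAA in the Week 48 window (5%, 10%, 20%).
- t: week of the last NSAA. The schedule in SAP Table 1 makes this Week 0, 12, 24 or 36.
- q: share of the missing boys' later losses that the zero rule still captures (0 to 1).
- Loss occurs at a constant hazard, with no recovery, and missing boys decline at the same rate as the others.

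**Formulas**

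Loss already visible at the last assessment: c = 1 − (1 − p)^(t/48).

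LOCF estimate = (1 − m)p + m[c + q(p − c)], so the understatement is m(1 − q)(p − c).

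**Base case.** For p = 20%, c is 0 at Week 0, 5.43% at Week 12, 10.56% at Week 24 and 15.41% at Week 36. With the last visit equally likely at each, mean c = 31.39/4 = 7.85%, and p − c = 12.15 points.

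| m | LOCF, q = 0 | Understatement, q = 0 | q = 0.5 | q = 1 |
|---|---|---|---|---|
| 5% | 19.4% | 0.6 points | 0.3 | 0 |
| 10% | 18.8% | 1.2 points | 0.6 | 0 |
| 20% | 17.6% | 2.4 points | 1.2 | 0 |

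**Without baseline carry-forward.** If only Weeks 12, 24 and 36 can be carried, mean c = 31.39/3 = 10.46% and p − c = 9.54 points. The q = 0 understatement falls to 0.5, 1.0 and 1.9 points, with m now the share carried from a post-baseline visit.

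**Wider range.** At q = 0, with p = 10% to 30%, m = 5% to 20% and a single last week from 0 to 36, the understatement runs from about 0.1 point (p = 10%, m = 5%, Week 36: 9.88%) to 6.0 points (p = 30%, m = 20%, Week 0: 24.0%).

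**Missing boys decline at twice the hazard.** Their true loss is 1 − 0.8² = 36%. With m = 10%, overall true loss is 0.9 × 20 + 0.1 × 36 = 21.6%. For them c averages (0 + 10.56 + 20.00 + 28.45)/4 = 14.75%, so LOCF at q = 0 gives 18 + 1.475 = 19.5%. That is 2.1 points low, about 10% in relative terms.

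**The sign can reverse.** With p = 20%, m = 10%, last visit at Week 24, q = 1, and 20% of boys last seen at zero regaining the item, LOCF gives 20.0% against a true 19.8%.

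**The alternatives on the same inputs**

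- Observed case: 20.0% in the base case (no bias). In the doubled-hazard case it is 20.0% against 21.6%, which is 1.6 points low.
- Worst case (base case): 0.95 × 20 + 5 = 24%; 0.9 × 20 + 10 = 28%; 0.8 × 20 + 20 = 36%. In the doubled-hazard case with m = 10% it is again 28%, above the true 21.6%.
- Kaplan-Meier time to first zero: about 20.7% against 21.6% in the doubled-hazard case.

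**The case against.** The strongest reply is that the SAP already deals with the most informative cases. An item a boy cannot do because of progression or loss of ambulation is scored zero before LOCF is reached, and a last score of zero is carried forward as a loss. The Premature-Discontinuation Visit includes the NSAA, so the carried value should date from exit, and an exit assessment from day 295 onward within the window is an observed Week 48 value. Some missingness comes from study closure or commercial switching and need not track decline. In size, 1.2 points at 10% missing is small beside sampling error: with 20% loss in at most about 220 boys, the 95% margin is 1.96 × √(0.2 × 0.8/220) = 5.3 points.

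Most of this stands, and it limits the point. It does not remove it. Nothing in the SAP extends the zero rule to a boy who has left and loses the item later. Protocol section 9 only asks investigators to encourage the exit evaluations, and an exit before day 295 is still frozen at that date. Sampling error is also a different matter: a systematic shift does not shrink with more boys.

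Two stronger readings are tempting. A reader might infer that every boy with missing data is counted as having kept the function, or that a boy with only a baseline score is counted as no loss by construction. The zero rule and the carrying forward of zeros contradict the first. The second depends on baseline carry-forward, which the SAP neither permits nor excludes. A reader might also infer that the bias always favours ataluren. The table has no comparator, item loss is not among the natural-history comparisons in SAP section 8.3, and the sign can reverse if items are regained.

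A further fair objection is that observed-case analysis is not always closer to the truth. With doubled hazard, 10% missing and every last visit at Week 36, LOCF gives 20.8% and observed case 20.0% against 21.6%.

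**Conclusion.** The point holds in limited form. Where Week 48 item data are missing for reasons other than recorded inability from progression or loss of ambulation, LOCF assumes no further change and generally understates loss. With 20% true loss, 5% to 20% missing, constant hazard and last visits spread over Weeks 0 to 36, the understatement is about 0.6 to 2.4 points if the zero rule catches none of the later losses, and zero if it catches all. Neither the rates nor q can be set from the documents. The deterioration premise in Protocol section 13.4.3 is stated for untreated patients, which is one more reason to say generally rather than always.

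No type I error or power is involved, because the table is descriptive, single-arm and secondary. The weakness is that a rule with a usual direction of error is the only analysis, and nothing shows how often it was applied. This is a worthwhile, cheap improvement and does not threaten the study's conclusions on safety.

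**What to change.** In SAP section 5.8.5, replace the LOCF sentence with the following:

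- **Main row:** observed-case proportion with loss at Week 48, keeping the zero rule, and showing for each item the number assessed in the Week 48 window and the number missing.
- **Worst-case row:** missing boys with a non-zero baseline counted as loss.
- **LOCF:** if kept at all, a sensitivity row only, with no baseline score carried forward for boys without a post-baseline NSAA.
- **Clarification:** state whether the zero rule applies after a boy has left the study, and on what evidence.
- **Kaplan-Meier time to first zero:** optional and supportive only. It estimates ever reaching zero by Week 48 rather than being at zero at Week 48, and it assumes non-informative censoring. It also counts transient zeros. With an assumed 1% chance of one at each of four visits and 20% true loss, it gives 1 − 0.8 × 0.99⁴ = 23.2%, against 1 − 0.8 × 0.99 = 20.8% at zero at Week 48.

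The item-loss table and its missing-data rule should also be listed in SAP section 7.

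The cost is a few SAP lines and extra table rows, using data already scheduled every 12 weeks through Week 48. The observed-case denominator will be smaller, and some bias remains if drop-out is related to decline. The worst-case row bounds that bias, though loosely when many boys are missing.
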